#### Decentration

O Decentration as determined at all post-operative scheduled visits starting at 7-14 days post-operative. Centration of the IOPCL AMD-MAG (using the PCIOL as a reference point) confirmed during slit lamp examination and defined as uniform exposed area of the PCIOL outside of the IOPCL AMD-MAG at the vertical and horizontal meridians between ≥ 0.25 mm and ≤ 0.75 mm.

#### • Adverse Events

Counts and percentages for incidence of cumulative and persistent intraoperative and postoperative adverse events.

• Secondary Surgical Interventions

Counts and percentages for incidence of secondary surgical interventions (e.g., removal of interlenticular opacity, repositioning of IOPCL, explant of IOPCL, repositioning of PCIOL) (excluding Nd:YAG treatments for PCO).

#### 3.3 Other Clinical Outcomes

- Visual acuity parameters (BCDVA, BCNVA, UCDVA, UCNVA)
- MRSE stability
- Add power
- Slit lamp examination including assessment capsular stability, decentration and tilt
- Gonioscopy
- Reading speed
- Contrast sensitivity (mesopic)
- Applanation intraocular pressure (IOP) using Goldmann

- Dilated fundus examination
- Optical coherence tomography (OCT)
- Spatial visualization between PCIOL and IOPCL using ultrasound biomicroscopy (UBM)
- Specular microscopy
- Visual symptoms (VFQ-25)
- External magnifier usage

#### 4 STUDY DESIGN

This will be a three (3) center US clinical trial, in which a maximum of 10 subjects will be implanted unilaterally with the IOPCL AMD-MAG and followed for 12 months.

The subjects who might be eligible are potentially interested in participating and have provided their informed consent will be examined preoperatively to obtain a medical history and to establish a baseline for their ocular condition. Qualified subjects who provide written consent will be enrolled into the study.

Subjects will undergo IOPCL implantation. Postoperatively, subjects will undergo a complete ophthalmic evaluation at regularly scheduled intervals in accordance with study protocol.

An Investigational Device Exemption (IDE) application will be submitted on clinical outcomes when all enrolled eyes have a chance of reaching the 4-6-month post-operative visit (Postop Form 4).

This study is being conducted in accordance with 21CFR, Parts 50, 54, 56 and 812.42 (U.S.C 282(j)). ISO 14155 Clinical investigation of Medical Devices for Human Subjects, ISO 11979-7, and the ethical principles laid down in the Declaration of Helsinki.

## 5 ANALYSIS POPULATIONS

The analyses will include the data of all study eyes where implantation of IOPCL was attempted and/or successful.

## **6 STATISTICAL CONSIDERATIONS**

### 6.1 General Considerations

Descriptive statistics (mean, median, standard deviation, minimum, and maximum) will be used to summarize continuous variables. Frequencies and percentages will be used to summarize categorical variables.

Any analysis not described in this plan will be considered exploratory, and will be documented in the clinical study report (CSR) as a post hoc analysis or a change to the planned analysis.

# 6.2 Sample Size

Sample size is limited to maximum of 10 subjects (eyes) for this Early Feasibility Study (EFS).

## 6.3 Randomization and Masking

This study will not be randomized or masked.

#### 6.4 Data Transformations and Derivations

- Age in years (round down) will be calculated using informed consent date and birth date.
- Time variables based on two dates (e.g., Start Date and End Date), will be calculated as (End Date Start Date) (in days) unless otherwise specified in the planned analysis section. For example, the postoperative day = postoperative visit date lens implantation date (i.e. surgical date).
- The following unit conversion will be implemented unless otherwise specified:
  - $\circ$  Months = Days / 30.4375
  - $\circ$  Years = Days / 365.25

# 6.5 Handling of Dropouts and Missing Data

All data analyses will be conducted based on available data. No imputation will be performed.

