## 6.8 Timing of Analyses

An interim analysis will be performed when all enrolled subjects either have been seen for their 4-6 month visit, or have earlier exited from the study before the 4-6 month visit, or the visit window has closed for the 4-6 month visit (i.e., missed visit).

Interim safety summaries will be provided for annual reports based on regulatory requirement. Postoperative follow-up through 12 months on all implanted subjects will be completed as per protocol at which the final report analysis will be performed.

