## 7 PLANNED METHODS OF ANALYSES

## 7.1 Accountability and Disposition

Accountability of the eyes by visit will be provided based on ISO 11979-7:2018 for all eyes. Reasons for discontinuation of study will be summarized. The number and percentage of eyes and subjects in each analysis population will be summarized.

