## 7.4 Effectiveness Analysis

## 7.4.1 Primary Analyses of the Primary Effectiveness Endpoint

The proportion of eyes able to achieve 10 letters or more of uncorrected near visual acuity (at 14 cm) at 12 months from baseline will be summarized.

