# 7.5 Safety Analyses

The safety population will be used to summarize all safety endpoints. No imputation for the missing values will be performed.

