## 7.5.1 Preservation of BCDVA

The analysis of this clinical outcome will be based on the observed data of IOPCL AMD-MAG. The number and percent of IOPCL implanted eyes with a BCDVA loss of 2 or more lines (≥10 letters) at 12 months from preoperative will be derived.

Additionally, if needed, data listing or summary will be provided for eyes with a BCDVA loss of  $\geq 2$  lines from the best BCDVA before the corresponding visits.

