#### 7.5.2 Preservation of BCNVA

The analysis of this clinical outcome will be based on the observed data of IOPCL AMD-MAG. The number and percent of IOPCL implanted eyes with a BCNVA loss of 2 or more lines (≥10 letters) at 12 months from preoperative will be derived.

Additionally, if needed, data listing or summary will be provided for eyes with a BCNVA loss of  $\geq 2$  lines from the best BCNVA before the corresponding visits.

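### An attempted eye with failed or aborted implantation or an explant leaves the 12-month effectiveness proportions if it has no 12-month value, although SAP 5 includes it

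*SAP*

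**What the plan says.** SAP 5 sets one analysis population: "The analyses will include the data of all study eyes where implantation of IOPCL was attempted and/or successful". SAP 6.5 then sets one rule for missing values: "All data analyses will be conducted based on available data. No imputation will be performed".

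The primary analysis in SAP 7.4.1 summarises "The proportion of eyes able to achieve 10 letters or more of uncorrected near visual acuity (at 14 cm) at 12 months from baseline" (a gain of at least 10 letters, in the wording of Protocol 4.3). The target is at least 75% of eyes. The secondary proportions in SAP 7.4.2 have targets of 75% or 50%. Neither section states a denominator or gives an outcome to an eye without the lens.

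For safety, SAP 7.5 says "The safety population will be used to summarize all safety endpoints", a name that SAP 5 does not use. SAP 7.5.1 reports "The number and percent of IOPCL implanted eyes with a BCDVA loss of 2 or more lines", and SAP 7.5.2 reports "The number and percent of IOPCL implanted eyes with a BCNVA loss of 2 or more lines". The target in SAP 3.2 is below 5% for each.

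The protocol foresees eyes that end without the lens. The procedure may be aborted (12.1.2), the lens may be taken out during surgery (12.1.4) or explanted later (12.1.7), and failure to implant is a listed intraoperative adverse event (16.2). Protocol 14.1 and 15 schedule acuity visits after explantation, timed from removal. SAP 6.4 counts postoperative days from the implantation date.

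**The concern.** In a first feasibility study of an implant, a lens that could not be placed or had to come out is a result of the device or the procedure. The available-data rule treats it like a missed visit. The population definition keeps the eye in the study, but the proportion can lose it without saying so.

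The plan sets numerical targets, so readers will compare the headline percentages with them. With at most 10 eyes, one or two eyes leaving the denominator can move a result across the 75% line. The acuity-loss counts have a related gap: a never-implanted eye is left out by definition, even when it was measured at 12 months, although it went through the attempted surgery.

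For an explanted eye, the documents reviewed do not say whether an acuity measured after removal serves as the 12-month value. The same eye could be scored or dropped, and that choice would be made in an unmasked study (SAP 6.3).

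**Working it through.** **Inputs from the documents.** At most 10 eyes (SAP 6.2), a cap with no calculation behind it, so there is no plan figure to reproduce. Targets of at least 75% and at least 50% (SAP 3.1.1, 3.1.2) and below 5% (SAP 3.2).

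**Assumptions.** The documents give no rate of failed implantation or explant, so k = 1, 2 or 3 unscored eyes of 10 are shown. A lost eye is regarded as a non-responder.

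**75% target.** The responders needed among n eyes are ceil(0.75 × n), which is 8, 7, 6, 6 for n = 10, 9, 8, 7. With k eyes lost and s responders, the reading changes when s ≥ ceil(0.75 × (10 − k)) but s < 8.

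| Eyes lost | Needed if dropped | Needed over all 10 | Counts where the reading changes |
|---|---|---|---|
| 1 | 7 of 9 | 8 | 7/9 = 77.8% v 7/10 = 70% |
| 2 | 6 of 8 | 8 | 6/8 = 75.0% v 60%; 7/8 = 87.5% v 70% |
| 3 | 6 of 7 | 8 | 6/7 = 85.7% v 60%; 7/7 = 100% v 70% |

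The exact (Clopper-Pearson) 95% intervals overlap almost entirely: 7/9 40.0–97.2%, 7/10 34.8–93.3%; 6/8 34.9–96.8%, 6/10 26.2–87.8%. The change is in how the point estimate reads against its target.

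**50% target.** ceil(0.5 × n) is 5, 5, 4, 4 for n = 10, 9, 8, 7. One lost eye changes nothing. With two or three lost, only s = 4 is affected: 4/8 = 50% or 4/7 = 57.1%, against 4/10 = 40%.

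**Conditional illustration only.** Suppose k eyes are lost and unscored, and the others respond independently with an assumed probability p. The chance that the 75% reading changes is the sum of C(10−k, s) p^s (1−p)^(10−k−s) over the counts in the table. For k = 1 and p = 0.7 this is 36 × 0.7^7 × 0.3^2 = 0.267.

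| Eyes lost | p = 0.7 | p = 0.8 | p = 0.9 |
|---|---|---|---|
| 1 | 0.267 | 0.302 | 0.172 |
| 2 | 0.494 | 0.629 | 0.531 |
| 3 | 0.329 | 0.577 | 0.850 |

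These figures attach no probability to the losses themselves.

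**Acuity loss.** 1/n is below 5% only from n = 21, so with 10 or fewer eyes the target is met only at zero losses. If one never-implanted eye is measured and has lost 10 letters, SAP 7.5.1 as worded gives 0/9 (met), while all attempted eyes give 1/10 = 10% (missed). Leaving out an unharmed eye can raise the percentage when another eye has a loss, but at this size it cannot turn a met target into a missed one.

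**Which visit counts.** SAP 6.8 says "Postoperative follow-up through 12 months on all implanted subjects will be completed as per protocol", which names implanted subjects only. Protocol 14 speaks of subjects in general and may cover never-implanted eyes as well. Protocol 19.3.1 includes post-removal examinations in completion. None of these sections says which visit supplies the 12-month value for an eye without the lens.

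**The case against.** The strongest reply is that few eyes need be lost. Explanted eyes have scheduled UCNVA, BCNVA and BCDVA visits after removal, and Protocol 19.3.2 asks for follow-up of terminated subjects. On a plain reading, available-data analysis keeps an explanted eye that has a value in the window. This stands. A reader might infer that every explanted eye disappears, and the documents do not support that. The point covers only eyes without a 12-month value, and their number cannot be foretold.

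Second, the direction depends on the estimand: 7/10 is a miss only if the tenth eye is regarded as a failure. This also stands and is stated as a condition. For an eye in which the lens could not be placed or kept, it is the natural reading.

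Third, the failures are visible elsewhere. SAP 7.1 says "Accountability of the eyes by visit will be provided based on ISO 11979-7:2018 for all eyes" and summarises reasons for discontinuation. SAP 7.5.3, 7.5.4 and 7.5.6 report secondary interventions, successful delivery and adverse events, and SAP 7.4.4 shows UCNVA by visit. With 10 eyes a careful reader could rebuild the denominator. That lowers the weight, but it does not correct the headline proportion.

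Two further inferences go too far. Protocol 4.2 considers suspension at two intolerance explants at one site, so three sites could have one each without meeting that criterion. That is not a failure rate, and three explants are not three unscored eyes. One might also infer that the post-removal visits replace the original ones and leave a gap at 12 months. Protocol 15 refers to Appendix 2B for these visits, and that appendix is not in the text reviewed, so no gap can be asserted.

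**Conclusion.** The point holds in a limited form. The stated rule removes an attempted eye without a 12-month value from the effectiveness proportions. If the reason is failed or aborted implantation or explant, and such an eye is regarded as a failure, the removal can only raise the proportion. At the margin this matters for the 75% target with one lost eye (7 responders) or two (6 or 7), and for the 50% targets only from two lost eyes (4 responders). The restriction of the acuity-loss counts to implanted eyes and the undefined safety population are inconsistencies with SAP 5 in their own right.

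A reader might take the conditional probabilities of 17% to 85% as the risk of a wrong reading. They are not: they presuppose unscored losses and assumed response rates that the documents do not give. Nor is there a formal test whose error rate is affected. The weight is moderate to low, but the change is cheap and worth making before database lock.

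**What to change.** **SAP 7.4.** Use all attempted eyes as the denominator. Count failed or aborted implantation, or explant before 12 months, as non-response, whether or not a post-removal acuity exists, and state that this is an estimand choice. Show the available-case proportion beside it. Report eyes missing for reasons unrelated to the device separately, with best- and worst-case counts, and do not fix them as non-responders in the main row. Example: 10 attempted eyes, one explant, one subject who moved away and 6 responders give 6/10 to 7/10 (60–70%), with 6/8 = 75% as the available-case figure.

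**SAP 7.5, 7.5.1 and 7.5.2.** Define the safety population as the SAP 5 set. Report BCDVA and BCNVA loss on all attempted eyes with measured 12-month values, flag post-removal values, and state the number of eyes without a value.

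**Visits.** Reconcile SAP 6.4 and 6.8 with Protocol 14, 14.1 and 19.3.1, and with Appendix 2B, on which visit supplies the 12-month value for explanted and never-implanted eyes.

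**Cost.** SAP wording, one extra row per table and possibly a protocol clarification on visits. Reported rates may be less favourable: with two failures and 6 responders, 75% becomes 60%.

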# 6.6 Examination of Subgroups

Due to the small sample size, no subgroup analyses will be conducted.

#### 6.7 Covariates

Covariates are not considered for adjustment in the analyses.

## 6.8 Timing of Analyses

An interim analysis will be performed when all enrolled subjects either have been seen for their 4-6 month visit, or have earlier exited from the study before the 4-6 month visit, or the visit window has closed for the 4-6 month visit (i.e., missed visit).

Interim safety summaries will be provided for annual reports based on regulatory requirement. Postoperative follow-up through 12 months on all implanted subjects will be completed as per protocol at which the final report analysis will be performed.

## 7 PLANNED METHODS OF ANALYSES

## 7.1 Accountability and Disposition

Accountability of the eyes by visit will be provided based on ISO 11979-7:2018 for all eyes. Reasons for discontinuation of study will be summarized. The number and percentage of eyes and subjects in each analysis population will be summarized.

# 7.2 Demographic and Baseline Characteristics

Demographics, preoperative parameters, and operative parameters will be summarized descriptively by mean, standard deviation, median, minimum, and maximum for the continuous outcomes and by count and percentage for the categorical outcomes.

#### 7.3 Protocol Deviations

Major protocol deviations are those that represent a divergence from the protocol that could have a significant effect on the integrity of the study data, or on the subject's rights, safety, or welfare. Major protocol deviations also include exemptions to the study inclusion/exclusion criteria and will be summarized by category. A list of subjects with major protocol deviations will be presented.

## 7.4 Effectiveness Analysis

## 7.4.1 Primary Analyses of the Primary Effectiveness Endpoint

The proportion of eyes able to achieve 10 letters or more of uncorrected near visual acuity (at 14 cm) at 12 months from baseline will be summarized.

# 7.4.2 Primary Analyses of the Secondary Effectiveness Endpoints

The proportion of eyes able to achieve 20 letters or more of uncorrected near visual acuity (at 14 cm) at 12 months from baseline will be summarized.

- Change in UCNVA from baseline will be reported in lines including the following bins: loss of 15 or more letters, loss of 10 or more letters, loss of more than 5 letters, no change (within +/- 5 letters), gain of more than 5 letters, gain of 10 or more letters, gain of 15 or more letters, gain of 20 or more letters.
- The UCNVA value of the implanted eyes will be summarized descriptively by mean, standard deviation, median, minimum, and maximum at 1 month or later.

The proportion of eyes able to achieve 10 letters or more of uncorrected near visual acuity (at 14 cm) at 12 months from baseline BCNVA (at 30 cm, wearing the appropriate preoperative distance refractive correction in addition to +3.0D add).

• Change in UCNVA from baseline BCNVA will be reported in lines including the following bins: loss of 15 or more letters, loss of 10 or more letters, loss of more than 5 letters, no change (within +/- 5 letters), gain of more than 5 letters, gain of 10 or more letters, gain of 15 or more letters, gain of 20 or more letters.

The proportion of eyes able to achieve 20 letters or more of uncorrected near visual acuity (at 14 cm) at 12 months from baseline BCNVA (at 30 cm, wearing the appropriate preoperative distance refractive correction in addition to +3.0D add).

• Change in UCNVA from baseline BCNVA will be reported in lines including the following bins: loss of 15 or more letters, loss of 10 or more letters, loss of more than 5 letters, no

change (within +/- 5 letters), gain of more than 5 letters, gain of 10 or more letters, gain of 15 or more letters, gain of 20 or more letters.

The proportion of eyes able to achieve 10 letters or more of best corrected near visual acuity (at 14 cm) at 12 months from baseline BCNVA (at 30 cm, wearing the appropriate preoperative distance refractive correction in addition to +3.0D add).

• Change in BCNVA from baseline will be reported in lines including the following bins: loss of 15 or more letters, loss of 10 or more letters, loss of more than 5 letters, no change (within +/- 5 letters), gain of more than 5 letters, gain of 10 or more letters, gain of 15 or more letters, gain of 20 or more letters.

The proportion of eyes able to achieve 20 letters or more of best corrected near visual acuity (at 14 cm) at 12 months from baseline BCNVA (at 30 cm, wearing the appropriate preoperative distance refractive correction in addition to +3.0D add).

• Change in BCNVA from baseline will be reported in lines including the following bins: loss of 15 or more letters, loss of 20 or more letters, loss of more than 5 letters, no change (within +/- 5 letters), gain of more than 5 letters, gain of 10 or more letters, gain of 15 or more letters, gain of 20 or more letters.

## 7.4.3 Exploratory Effectiveness Endpoints

The following exploratory effectiveness endpoints will be evaluated for eyes that achieve  $\geq 20$  letters of improvement in UCNVA during preoperative simulation testing.

• Proportion of eyes (≥ 75%) achieving improved reading speed (at 40 cm) at 12 months from baseline defined as ≥ 2 lines/blocks of gain with a decrease in reading speed ≥ 1 minute and with overall improvement in critical point size

Change in reading speed will be reported as follows:

- Change in lines/blocks using the following bins: loss of 3 or more blocks, loss of 2 or more blocks, loss of more than 1 block, no change (within 1 block), gain of more than 1 block, gain of 2 or more blocks, gain of 3 or more blocks, gain of 4 or more blocks.
- Change in reading rate using the following bins: loss of 3 minutes or more, loss of 2 or more minutes, loss of more than 1 minute, no change (within 1 minute), gain of more than 1 minute, gain of 2 or more minutes, gain of 3 or more minutes, gain of 4 or more minutes.
- Change in critical point size using the following bins: loss of 3 or more point sizes, loss of 2 or more point sizes, loss of 1 point size, no change in point size, gain of 1 point size, gain of 2 or more point sizes, gain of 3 or more point sizes, gain of 4 or more point sizes.

Reading speed of the primary eyes will be summarized descriptively by mean, standard deviation, median, minimum, and maximum at 1 month or later.

• Proportion of eyes (≥ 75%) achieving independence from external magnifier usage at 12 months postoperatively

Independence from external magnifier usage will be reported using the following bins: continued usage of all external magnifier(s) used preoperatively (no change), deceased usage of 1 or more external magnifiers used preoperatively (partial independence); deceased usage of all external magnifiers used preoperatively (complete independence)

## 7.4.4 Additional Effectiveness Analyses

All the available monocular uncorrected distance visual acuity and monocular uncorrected near visual acuity at each protocol specified scheduled visit will be presented for the primary eyes. The categorical presentations will include the visual acuity of 75 letters or better, 70 letters or better, 65 letters or better, 60 letters or better, 55 letters or better, 50 letters or better, 45 letters or better, 40 letters or better, and fewer than 40 letters.

# 7.5 Safety Analyses

The safety population will be used to summarize all safety endpoints. No imputation for the missing values will be performed.

## 7.5.1 Preservation of BCDVA

The analysis of this clinical outcome will be based on the observed data of IOPCL AMD-MAG. The number and percent of IOPCL implanted eyes with a BCDVA loss of 2 or more lines (≥10 letters) at 12 months from preoperative will be derived.

Additionally, if needed, data listing or summary will be provided for eyes with a BCDVA loss of  $\geq 2$  lines from the best BCDVA before the corresponding visits.

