4.1. Safety Endpoints

- Preservation of BCDVA Proportion of eyes (< 5%) that lose two or more lines of BCDVA (≥10 letters on the ETDRS chart) at 12 months from baseline.
- Preservation of BCNVA Proportion of eyes (<5%) that lose two or more lines of BCNVA
 (≥10 letters on the Sloan Near Vision Chart at 14 cm) at 12 months from baseline.
- Incidence of secondary surgical intervention (SSI).
- Successful delivery of the IOPCL AMD-MAG as determined at all postoperative scheduled visits starting at 7-14 days post-operative.
 - No capsular tear
 - No visible damage to either the PCIOL or the IOPCL AMD MAG
 - o Uniform leaflet coverage of all IOPCL AMD MAG haptic tabs
- Long-term adherence and positional stability
 - O Gap: Minimal change in uniformity of the gap between consecutive scheduled visits at 1-2 months and later as determined by UBM measurements. Minimal change is defined as +/- 10 microns between visits is established and maintained using UBM imaging.
 - o Tilt:
- Tilt of the PCIOL as determined at all post-operative scheduled visits starting at 30-60 days post-operative. Minimal tilt of the PCIOL confirmed via penlight examination and defined as ≤ 10 degrees between the postoperative tilt of the PCIOL and the pre-operative tilt of the PCIOL.
- Tilt of the IOPCL AMD-MAG as determined at all post-operative scheduled visits starting at 30-60 days post-operative. Minimal tilt of the IOPCL AMD-MAG (using the PCIOL as a reference point) confirmed via penlight examination and defined as ≤ 10 degrees between the post-operative tilt of the. PCIOL and the postoperative tilt of the IOPCL AMD-MAG.
- O Decentration: Decentration as determined at all post-operative scheduled visits starting at 7-14 days post-operative. Centration of the IOPCL AMD-MAG (using the PCIOL as a reference point) confirmed during slit lamp examination and defined as uniform exposed area of the PCIOL outside of the IOPCL AMD-MAG at the vertical and horizontal meridians between ≥ 0.25 mm and ≤ 0.75 mm.
- Counts and percentages for incidence of cumulative and persistent intraoperative and post-operative adverse events
- Counts and percentages for incidence of secondary surgical interventions (e.g., removal
 of interlenticular opacity, repositioning of IOPCL, explant of IOPCL, repositioning of
 PCIOL) (excluding Nd:YAG treatments for PCO).

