the edge of the underlying PCIOL. Confirm the capsule is stable by applying gentle pressure to all three seated haptic. If capsular stability is not confirmed, the IOPCL AMD-MAG should be removed (refer to Section 12.1.7 for removal instructions). Once stability is confirmed, perform thorough irrigation/aspiration of OVD and any displaced cortical material.

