## 7.5.7 Other Safety Analyses

## 7.5.7.1 Best-corrected Distance Visual Acuity

All the available monocular best-corrected distance visual acuity at each protocol specified scheduled visit will be presented for the implanted eyes. The categorical presentations will include the visual acuity of 20/16 or better, 20/20 or better, 20/25 or better, 20/32 or better, 20/40 or better, 20/50 or better, 20/63 or better, 20/80 or better, and worse than 20/80.

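### The SAP includes every attempted eye in its analyses but counts vision loss only in implanted eyes, and never defines its safety population

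*SAP*

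**What the plan says.** **Population.** SAP section 5 describes one set: "The analyses will include the data of all study eyes where implantation of IOPCL was attempted and/or successful". It makes no exception for any endpoint. SAP 7.5 then says "The safety population will be used to summarize all safety endpoints", but neither section 5 nor any other section defines that population. SAP 7.1 speaks of each analysis population, as if there were several.

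**Endpoint.** Protocol 4.1 defines the distance-acuity endpoint as "Proportion of eyes (< 5%) that lose two or more lines of BCDVA (≥10 letters on the ETDRS chart) at 12 months from baseline". The near-acuity endpoint has the same form, and SAP 3.2 repeats both. None of these definitions is limited to implanted eyes.

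**Analysis.** The restriction appears only at the analysis step. SAP 7.5.1 derives "The number and percent of IOPCL implanted eyes with a BCDVA loss of 2 or more lines" and SAP 7.5.2 derives "The number and percent of IOPCL implanted eyes with a BCNVA loss of 2 or more lines". The acuity distributions in 7.5.7.1 and 7.5.7.2 "will be presented for the implanted eyes". The SAP does not define an implanted eye, and 7.5.1 and 7.5.2 do not state the denominator. By contrast, SAP 7.5.3 to 7.5.6 (secondary interventions, delivery, stability, adverse events) refer simply to eyes.

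**Surgery without a lens in place.** Protocol 12.1.2 provides for stopping the procedure when the lens/bag complex moves too much. Protocol 16.2 lists failure to implant the lens as an intraoperative adverse event. Protocol 12.1.4 adds: "If capsular stability is not confirmed, the IOPCL AMD-MAG should be removed".

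**The concern.** An eye in which surgery was begun but no lens was implanted has been exposed to the study procedure. Section 5 includes it. The literal wording of 7.5.1 and 7.5.2 leaves it out, and it does so even when the 12-month acuity was measured, so this is a counting rule and not a missing-data problem.

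Two analysts working from the same SAP could therefore report different vision-loss rates. The implanted-only reading can only remove losses that occurred in non-implanted eyes, so where it changes whether the target is met, it does so in the device's favour. If the denominator is settled after the data are seen, that choice could decide whether the prespecified target is reported as met.

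**Working it through.** The plan gives no power, alpha or derived sample size, so there is no figure of its own to reproduce. The check compares the readings of the SAP on one example.

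**Inputs**
- At most 10 eyes (SAP 6.2).
- Target: under 5% of eyes losing 10 or more letters at 12 months (Protocol 4.1, SAP 3.2).
- Available data only, no imputation (SAP 6.5 and 7.5).
- Assumption for illustration: 10 attempted eyes, one never implanted. That eye loses 10 or more letters and has a known 12-month value; no other eye has such a loss.

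**Step 1: how many losses the target allows.** One loss among n eyes gives 1/n, which is below 0.05 only if n is above 20. At n = 10 it is 10%. The target is therefore met only with zero counted losses.

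**Step 2: the rate under each reading**, with Clopper-Pearson 95% limits. For x = 0 the upper limit is 1 − 0.025^(1/n). For x = 1 the lower limit is 1 − 0.975^(1/n), and the upper limit solves (1−p)^n + n·p·(1−p)^(n−1) = 0.025.

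| Reading | Losses/eyes | Rate | 95% CI | Under 5%? |
|---|---|---|---|---|
| Attempted eyes throughout (SAP 5) | 1/10 | 10% | 0.3% to 44.5% | No |
| Implanted eyes throughout (7.5.1 read literally) | 0/9 | 0% | 0% to 33.6% | Yes |
| Implanted eyes in the numerator, attempted in the denominator | 0/10 | 0% | 0% to 30.8% | Yes |

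With two such eyes, the first two readings give 2/10 = 20% (2.5% to 55.6%) and 0/8 = 0% (0% to 36.9%).

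**Step 3: how often the question could arise.** The documents give no rate of failed implantation. If it is p per eye and eyes are independent, the chance of at least one failure in 10 is 1 − (1−p)^10: 40% at p = 5%, 65% at 10% and 89% at 20%. These are assumed values, and they give the chance of a failed implantation, not of a vision loss.

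**Step 4: whether the 12-month value would exist.** Protocol 14.1 and 15 schedule acuity after lens removal out to 330-420 days, so a lens removed during the same surgery can have a 12-month value. No schedule is specific to an eye that never received the lens, and SAP 6.8 promises 12-month follow-up for implanted subjects. If the eye in the example had no 12-month value, the available-data rule would give 0/9 even on the section 5 set. Changing the population wording alone would not be enough.

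**The case against.** The strongest reply is that nothing is actually excluded. Section 5 is the only population described, it covers attempted eyes without exception, and the natural reading is that the safety population is that same set. On this view, implanted eyes in 7.5.1 is loose wording; the SAP also speaks of primary eyes without defining them. This stands to the extent that a reader who infers a settled exclusion goes further than the documents do. They contain a conflict, with the broad rule in section 5 and the narrow one in the sections that produce the numbers. It does not remove the need to resolve that conflict.

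Three other inferences also go too far:

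- **That non-implanted eyes are the likeliest to lose vision.** The documents do not support this. The stop in Protocol 12.1.2 comes before capsule dissection and is meant to spare the zonules.
- **That every serious intraoperative event means no implantation.** Protocol 16.2 lists capsular rupture, vitrectomy and retinal detachment without saying that the lens is then withheld. Likewise, a lens placed and then removed under 12.1.4 may count as implanted, because the term is undefined. Only never-implanted eyes are clearly affected.
- **That the harm would be hidden.** SAP 7.5.6 tabulates adverse events per eye, including intraoperatively. The supplementary listings in 7.5.1 and 7.5.2 also refer to eyes without the restriction, though only if needed. Those tables do not replace the endpoint, however: the postoperative list in Protocol 16.3 has no separate item for a 10-letter loss.

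Finally, this is a descriptive feasibility study, and no decision rule rests on the 5% figure. The suspension criteria in Protocol 4.2 use severe ocular injuries and explants. That lowers the severity.

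**Conclusion.** The concern holds as an internal conflict: SAP 5 and 7.5 on one side, and SAP 7.5.1, 7.5.2, 7.5.7.1 and 7.5.7.2 on the other, with both the safety population and the implanted eye left undefined. Its reach is an attempted but never-implanted eye; an eye whose lens is removed in the same surgery is ambiguous.

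One such eye with a loss of 10 or more letters would be enough to decide whether the target is met (0% against 10%). That contrast assumes that the eye exists, that its 12-month acuity was measured, and that stopping after the incision counts as an attempt. The documents give no rate for the first, do not secure the second, and do not say at which step an attempt begins.

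This should be fixed before results are known. It falls short of a must-fix because the analyses are descriptive, nothing is decided by the 5% threshold, and the adverse event tables would still report the event.

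**What to change.** 1. In SAP 5, name the set already described there as the safety population, for example: *The safety population is every study eye with attempted implantation, regardless of whether a lens remained in the eye at the end of surgery.* Say at which step an attempt begins.
2. In SAP 7.5.1 and 7.5.2, use this population for both numerator and denominator. Use it also for the presentations in 7.5.7.1 and 7.5.7.2. An implanted-only rate may be added as a second line, with implanted defined so that same-surgery removal is covered.
3. Reconcile SAP 6.8 and the visit schedules in Protocol 14 and 14.1 with this population, and state which visit supplies the 12-month acuity of a never-implanted eye.
4. Beside each rate, report the number of attempted eyes without a 12-month value.

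Items 1, 2 and 4 need SAP wording only. Item 3 may also need a protocol clarification and 12-month data for the few eyes concerned. The price is that the reported loss rate may be less favourable.
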